#### Competency Scores

Sub-scores	# of Items	Score Range	Items
Activity	6	(0-15)	I.A, B, II.A, B, IV A, B
Social	6	(0-14)	III.A, B, V.1, 2, VI. A, B
School	4	(0-6)	VII. 1, 2,3,4
Total	16	(0-35)	Sum of 3 previous scores

#### Syndrome/ Problems Scores

Syndrome scale	#of items	Score Range	Items
Anxious/Depressed	13	(0-26)	14,29,30,31,32,33,35,45,50,52,71, 91,112
Withdrawn/Depressed	8	(0-16)	5,42,65,69,75,102,103,111
Somatic Complaints	11	(0-22)	47,49,51,54,56a,56b,56c,56d,56e, 56f,56g
Internalizing	32	(0-64)	sum of 3 previous scores
Rule-Breaking Behavior	17	(0-34)	2,26,28,39,43,63,67,72,73,81,82,9 0,96,99,101,105,106
Aggressive Behavior	18	(0-36)	3,16,19,20,21,22,23,37,57,68,86,8

			7,88,89,94,95,97,104
Externalizing	35	(0-70)	sum of 2 previous scores
Social Problems	11	(0-22)	11,12,25,27,34,36,38,48,62,64,79
Thought Problems	15	(0-30)	9,18,40,46,58,59,60,66,70,76,83,84,85,92,100
Attention Problems	10	(0-20)	1,4,8,10,13,17,41,61,78,80
Total	120	(0-240)	Sum of all problem items scores, including: Internalizing Syndromes, Externalizing Syndromes, Social Problem, Thought Problem, Attention Problem, and 17 not yet accounted for problems

Additionally, the borh CBCL results for each subject will be converted to a standardized T-score and classified at baseline and at each evaluation as normal, borderline clinical, or clinical, based on the thresholds provided in the CBCL manual. These classifications and their change from baseline will be presented in tables.

### Lafayette Grooved Pegboard Test (LGPT)

Time taken to perform the Lafayette Grooved Pegboard Test correctly (i.e. inserting 25 pegs for 8 years or older or 10 pegs for under 8 years old for each hand, ranges up to 300 seconds) will be summarized by visit. If the task cannot be completed correctly at 300 seconds, 300 seconds will be recorded.

Total number of pegs correctly placed and total number of pegs dropped will also be summarized separately for each hand by visit.

Total score for each hand (Trites) will be calculated as time to complete the test + total number of pegs dropped + total number of pegs correctly placed.

All summaries will be calculated by each age group (for 8 years or older, for under 8 years old) separately.

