#### 5.1.2 Secondary Endpoints

The following endpoints will be analyzed:

1. The relationship between plasma levels of perampanel and efficacy endpoints (ie, change in average seizure frequency over 28 days, responder probability, and the proportion of subjects who are seizure-free in the Maintenance Period of the Core Study) separately for each seizure type
2. The relationship between plasma levels of perampanel and cognition endpoints including change from baselines in ABNAS, CBCL, and LGPT. In addition, depending on the AE data, the relationship between plasma levels of perampanel and select AEs will be assessed
3. Change from baseline at Week 23 and Week 52 in ABNAS, CBCL, and LGPT
4. Changes from baseline at Week 23 and Week 52 in growth and development parameters (height, weight, thyroid, and IGF-1)
5. Change from baseline in EEG and the frequency of EEG abnormalities during awake and sleep state
6. Proportion of subjects (aged 6 or older at time of consent/assent) with any treatment-emergent reports of suicidal ideation and behavior on the C-SSRS and intensity of these behaviors assessed using C-SSRS scores
7. The median percent change in seizure frequency per 28 days during Treatment Phase (Titration Period and Maintenance Period) of the Core Study, and during the long-term treatment (up to 52 weeks) relative to the Pretreatment Phase. Seizure frequency will be based on the number of seizures per 28 days, calculated as the number of seizures over the entire time interval divided by the number of days in the interval and multiplied by 28
8. Proportion of responders (25% responders defined as a decrease in 28-day seizure frequency of equal or greater than 25% compared to baseline seizure frequency; 50% responders defined as a decrease in 28-day seizure frequency of equal or greater than 50% compared to baseline seizure frequency; 75% responders defined as a decrease in 28-day seizure frequency of equal or greater than 75% compared to baseline seizure frequency) during Maintenance Period of Core Study, and during the long term treatment (up to 52 weeks)
9. Proportion of subjects who are seizure-free during Maintenance Period of Core Study, and during the long-term treatment (up to 52 weeks)
10. CGI of Change

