**Lafayette Grooved Pegboard Test (LGPT)**

Time taken to perform the Lafayette Grooved Pegboard Test correctly (i.e. inserting 25 pegs for 8 years or older or 10 pegs for under 8 years old for each hand, ranges up to 300 seconds) will be summarized by visit. If the task cannot be completed correctly at 300 seconds, 300 seconds will be recorded.

Total number of pegs correctly placed and total number of pegs dropped will also be summarized separately for each hand by visit.

Total score for each hand (Trites) will be calculated as time to complete the test + total number of pegs dropped + total number of pegs correctly placed.

All summaries will be calculated by each age group (for 8 years or older, for under 8 years old) separately.

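### The LGPT total score adds pegs placed to a time capped at 300 s, so its change can have the wrong sign for some children who time out

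*SAP*

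**What the plan says.** The LGPT part of SAP 5.6.6 defines a completed test as "inserting 25 pegs for 8 years or older or 10 pegs for under 8 years old for each hand". For a test that is not finished it sets the time: "If the task cannot be completed correctly at 300 seconds, 300 seconds will be recorded". The total score for each hand is then "time to complete the test + total number of pegs dropped + total number of pegs correctly placed", with a plus sign on every term.

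The SAP does not say whether a higher total is better or worse, and it has no separate rule for the total score of a timed-out test. The individual components are also planned: completion time by visit, and "Total number of pegs correctly placed and total number of pegs dropped will also be summarized separately for each hand by visit". The two test versions are kept apart: "All summaries will be calculated by each age group (for 8 years or older, for under 8 years old) separately". Section 5.6.6 of the extension SAP repeats all of this.

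Item 3 of the secondary endpoints (SAP 5.1.2, matching protocol 9.7.1.1.2) is "Change from baseline at Week 23 and Week 52 in ABNAS, CBCL, and LGPT". It does not say which LGPT measure is meant.

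**The concern.** Among children who finish, pegs placed is a constant (25 or 10), so adding it changes nothing in their ranking: a longer time or more drops means a higher score. That implies higher is worse.

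For a child who times out, time is also a constant. Only drops, which are bad, and correct placements, which are good, can still move the score, and they carry the same sign. Whichever direction is declared to be better, one of the two points the wrong way.

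The LGPT is the protocol's measure of visuomotor skills (protocol 7.2) and is analysed as a safety variable. Children who cannot finish in 300 s are plausibly those for whom a drug effect on dexterity matters most. If such a child gets worse and the total score falls, a table of change in that score shows improvement.

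**Working it through.** **Inputs, all from the LGPT part of SAP 5.6.6.** Pegs needed: P = 25 (age 8 or older) or P = 10 (under 8). Recorded time: T, set to 300 for uncompleted tests. Drops: D. Pegs correctly placed: K. Score: S = T + D + K. The SAP gives no worked score, so there is no figure of its own to reproduce. I take an uncompleted test to have K < P, and use whole seconds and equal drops (D = 0 in the examples).

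**1. Timed-out tests.** T = 300, so S = 300 + D + K. One more correct peg adds 1 to S.

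| Version | Fewest pegs | Middle | Most pegs | Range |
|---|---|---|---|---|
| 25 pegs | K = 0: 300 | K = 12: 312 | K = 24: 324 | 24 |
| 10 pegs | K = 0: 300 | K = 5: 305 | K = 9: 309 | 9 |

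A child who times out at both visits and falls from 20 to 5 of 25 pegs goes from 320 to 305. That is a change of −15, the direction of improvement.

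**2. Finishing against timing out.** A finisher has K = P, so S = T + D + P. At equal drops this exceeds the score of a time-out with K pegs when T + P > 300 + K, that is:

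- 25 pegs: T > 275 + K
- 10 pegs: T > 290 + K

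Examples:

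- 25 pegs: a time-out with 5 placed scores 300 + 5 = 305; all 25 in 290 s scores 290 + 25 = 315. A child who goes from the first to the second is recorded as 10 points higher, although the test is now completed.
- 10 pegs: a time-out with 2 placed scores 302; a finish in 295 s scores 295 + 10 = 305.

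**3. How much of the score space is affected.** Take every pairing of a finish at T = 1 to 299 s with a time-out at K = 0 to P − 1.

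- 25 pegs: inverted pairs are the sum of (24 − K) over K = 0 to 24, which is 300, of 299 × 25 = 7475 (4.0%).
- 10 pegs: the sum of (9 − K) over K = 0 to 9, which is 45, of 299 × 10 = 2990 (1.5%).

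These count possible combinations. They are not expected frequencies in patients.

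**4. Replacing pegs placed by pegs not placed, for every test.** S′ = T + D + (P − K). Finishers score T + D, so a finish at 299 s with no drops scores 299. Timed-out tests with no drops run from 325 (0 placed) down to 301 (24 placed) for 25 pegs, and from 310 down to 301 for 10 pegs. No inversion is left at equal drops.

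**The case against.** The strongest reply is that the plan already shows the information correctly elsewhere. Time, pegs placed and pegs dropped are each to be summarized by visit and by age group, so a timed-out child who places more pegs appears as improved in the pegs-placed table. The total score is one of four derived LGPT measures, the endpoint does not name it, and no test or decision rule rests on it. All of this stands, and it limits the importance of the point. It does not make the composite interpretable for timed-out tests.

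Two stronger readings are tempting, and the documents support neither.

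- A reader might infer that the sign of change is reversed for impaired children in general. It is not. At equal drops, a child who goes from timing out to finishing in 275 s or less (25 pegs) or 290 s or less (10 pegs) is never scored as worse, and drops always count in the expected direction. Unequal drops can widen or narrow the reversal.
- A reader might infer that the sponsor added its own 300 s cap to a published sum. The SAP gives only a name for the score, and neither SAP's reference list contains a source for it. Whose cap it is, and whether the source has a rule for time-outs, cannot be checked. The algebra needs neither claim.

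**Conclusion.** The point holds in a limited form. As written in both SAPs, the total score is not coherent for timed-out tests, and its change can have the wrong sign in two situations: time-out at both visits with a change in pegs placed, and a move between timing out with K pegs and a finish slower than 275 + K s (25 pegs) or 290 + K s (10 pegs). Among timed-out tests the distortion is at most 24 or 9 points, on a base of 300.

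This assumes equal drops, and that higher is worse, which the time and drops terms imply but the SAP does not state. How many children are affected is unknown, because the documents give no time-out rate. With a descriptive analysis and separate component summaries, this is a desirable correction and not an essential one.

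**What to change.** Change the total-score rule in both SAPs, in one of two ways.

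1. Compute the total score for completed tests only, show uncompleted tests as timed out with the number of pegs placed, and report the number timed out at each visit.
2. If one score for all children is wanted, define it as time + drops + pegs not placed for every test, finishers included, and again report the number timed out at each visit.

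In either case, state that a higher score is worse.

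Option 2 must not be applied to timed-out tests alone. If finishers keep their added 25, a finish in 290 s still scores 315 while a time-out with 20 pegs scores 300 + 5 = 305. Finishing then scores worse than failing, in a pair that the current formula orders correctly (315 against 320). On the grid used above, that half-change leaves 276 inverted pairs in place of 300 (25 pegs) and 36 in place of 45 (10 pegs).

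The cost is about one sentence in each SAP, using data already collected. The downside is small: under option 1 the total score is undefined for timed-out tests, and under option 2 it departs from the named score.

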### Growth parameter

The actual value and change from baseline in growth parameter (height, weight, TSH, fT3, fT4 and IGF-1) will be summarized by visit. Height and weight will present summary statistics for overall percentile and overall z-score.

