9.5.1.5.3 LABORATORY MEASUREMENTS

Clinical laboratory tests to be performed, including hematology, chemistry, and urinalysis, are summarized in [Table 3](#). Subjects should be in a seated or supine position during blood collection. The Schedule of Procedures/Assessments ([Table 4](#)) shows the visits and time points at which blood for clinical laboratory tests and urine for urinalysis will be collected in the study (Core Study).

Table 3 Clinical Laboratory Tests

Category	Parameters
Hematology	Hematocrit, hemoglobin, platelets, RBC count, and WBC count with differential (basophils, eosinophils, lymphocytes, monocytes, neutrophils) (revised per Amendment 01)
Chemistry	
Electrolytes	Chloride, potassium, sodium
Liver function tests	Alanine aminotransferase, alkaline phosphatase, aspartate aminotransferase, gamma glutamyl transpeptidase, direct bilirubin, total bilirubin
Renal function tests	Blood urea/blood urea nitrogen, creatinine
Other	Albumin, calcium, cholesterol, globulin, glucose ^a , lactate dehydrogenase, phosphorus, total protein, triglycerides ^a , uric acid
Urinalysis	Bacteria, casts, crystals, epithelial cells, glucose, ketones, occult blood, pH, protein, RBCs, specific gravity, WBCs, Urine drug screen ^b (revised per Amendment 01)

RBC = red blood cell, WBC = white blood cell.

- a: Fasting samples to be taken at baseline and at end of treatment or early discontinuation, with fasting window (interval) between 2 and 4 hours.
- b: To be performed only at baseline. (revised per Amendment 01)

Clinical laboratory tests during the Core Study and Extension A will be performed by a central laboratory. (revised per Amendment 03) All blood and urine samples will be collected and sent to the central laboratory on the day of collection unless otherwise instructed. In cases of a safety concern, blood samples will be split (or 2 samples drawn) to allow a local laboratory analysis in addition to the central laboratory.

A laboratory abnormality may meet the criteria to qualify as an AE as described in this protocol (see [Section 9.5.1.5.1](#) and the CRF Completion Guidelines). In these instances, the AE corresponding to the laboratory abnormality will be recorded on the AE CRF.

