9.5.2 Schedule of Procedures/Assessments – Core Study

9.5.2.1 Schedule of Procedures/Assessments

[Table 4](#) presents the schedule of procedures/assessments for the Core Study.

Table 4 Schedule of Procedures/Assessments in Study E2007-G000-311: Core Study

Phase	Pre-Treatment	Treatment Phase									Early Discontinuation ^d	Unscheduled
	Screening/Baseline	Titration ^a				Maintenance ^b				Follow-up ^{b,c}		
Visit	1	2	3	4	5	6	7	8	9			
Week	From up to -4 weeks ±3 days to Week 0 (outside of Japan) -4 weeks ±3 days to Week 0 (Japan only) (revised per Amendment 02)	0	2	5	8	11	15	19	23	27		
Procedures/Assessments												
Demography	X											
Informed consent/assent	X											
Inclusion/exclusion criteria	X	X										
Medical history	X											
Epilepsy medical history	X											
Prior/concomitant medication(s)	X	X	X	X	X	X	X	X	X	X	X	X
Prior/concomitant AED(s)	X	X	X	X	X	X	X	X	X	X	X	X
Neurological examination ^e	X								X	X	X	
Physical examination ^e	X								X	X	X	
Vitals ^f and weight ^g	X	X	X	X	X	X	X	X	X	X	X	X
Height ^g		X							X		X	
Adverse events	X	X	X	X	X	X	X	X	X	X	X	X
Study drug compliance			X	X	X	X	X	X	X		X	X
Dispense study drug		X	X	X	X	X	X	X	X ^h			X ⁱ
Retrieve unused study drug			X	X	X	X	X	X	X		X	X ⁱ
Dispense subject's diary	X	X	X	X	X	X	X	X	X ^h			X
Retrieve and review diary		X	X	X	X	X	X	X	X	X	X	X
Clinical laboratory tests ^j	X ^k					X			X ^k	X	X	X

Table 4 Schedule of Procedures/Assessments in Study E2007-G000-311: Core Study

Phase	Pre-Treatment	Treatment Phase									Early Discontinuation ^d	Unscheduled
		Screening/Baseline	Titration ^a				Maintenance ^b			Follow-up ^{b,c}		
Visit	1	2	3	4	5	6	7	8	9			
Week	From up to -4 weeks ±3 days to Week 0 (outside of Japan) -4 weeks ±3 days to Week 0 (Japan only) (revised per Amendment 02)	0	2	5	8	11	15	19	23	27		
Procedures/Assessments												
Thyroid (TSH, fT3, fT4) and IGF-1 testing	X								X		X	
Serum β-hCG (or hCG) test ^l	X											
Urine pregnancy test ^l		X	X	X	X	X	X	X	X	X	X	X
C-SSRS ^m	X	X	X	X	X	X	X	X	X	X	X	X
12-lead ECG ⁿ	X								X	X	X	X ^o
EEG ^p	X								X		X	X ^o
Perampanel PK sampling (plasma) ^{q,r}							X	X	X		X	X
Telephone call ^s		X	X	X	X	X	X	X				
ABNAS ^t	X ^u	X					X		X		X ^v	
Lafayette Grooved Pegboard Test	X ^u	X					X		X		X ^v	
Child Behavior Checklist		X							X		X	
EQ-5D-Y		X							X		X	
Clinical Global Impression		X							X		X	
Disposition		X							X		X	
IxRS	X	X	X	X	X	X	X	X	X	X	X	X

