- g: Weight and Height (without shoes) will be measured. Three measurements should be taken at each visit. Each measurement should be recorded as a separate entry on the Vital Sign eCRF.
- h: Only for those subjects who continue into Extension A.
- i: Unused study drug to be retrieved and study drug dispensed only for subjects requiring dose increases at Unscheduled Visits.
- j: Clinical laboratory tests include hematology, blood chemistry including lipid panel, and urinalysis.
- k: Fasting lipid and glucose samples to be taken at baseline and at end of treatment or early discontinuation, with fasting window (interval) between 2 and 4 hours.
- l: Female subjects age 8 years old and above, or of childbearing potential, only. If urine can not be obtained for pregnancy testing after screening, a serum pregnancy test will be performed. (revised per Amendment 01)
- m: Only for subjects aged 6 years and older at the time of consent/assent.
- n: If subject has a normal ECG baseline reading, but during any visit thereafter, the QT is measured as greater than 450 ms, 3 consecutive ECGs separated by 5 to 10 minutes will be performed to confirm the abnormality.
- o: During Unscheduled Visits, ECG or EEG will only be done if the results from the previous visit were deemed clinically significant by the investigator.
- p: EEG will be performed at awake and sleep state for all subjects.
- q: One blood sample (approximately 1 mL) for determination of perampanel plasma concentrations will be collected at any time during each of the specified visits.

Table 4 Schedule of Procedures/Assessments in Study E2007-G000-311: Core Study

Phase	Pre-Treatment	Treatment Phase									Early Discontinuation ^d	Unscheduled
	Screening/Baseline	Titration ^a				Maintenance ^b				Follow-up ^{b,c}		
Visit	1	2	3	4	5	6	7	8	9			
Week	From up to -4 weeks ±3 days to Week 0 (outside of Japan) -4 weeks ±3 days to Week 0 (Japan only) (revised per Amendment 02)	0	2	5	8	11	15	19	23	27		
Procedures/Assessments												

- r: Additional blood (approximately 1 mL/sample) will be drawn at the 1st report (where possible) of a serious adverse event or severe unexpected AE and at its resolution. (revised per Amendment 01)

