## 5 STATISTICAL METHODS

All descriptive statistics for continuous variables will be reported using mean, standard deviation (SD), median, minimum and maximum. Categorical variables will be summarized as number (percentage) of subjects. All summaries will be produced by age cohort (4-<7 and 7-<12), disease cohort (POS, PGTC, GTC) and inducer status (inducer, non-inducer) except TEAE summary by speed of titration. All analysis will be conducted for Japanese POS subjects in Japanese sites (Country=Japan).

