## 5.6 Safety Analyses

All safety analyses will be performed on the Safety Analysis Set (SAS). Safety data will be summarized on an “as treated” basis using descriptive statistics (eg, n, mean, standard deviation, median, minimum, maximum for continuous variables; n [%] for categorical variables). Safety variables include TEAEs, clinical laboratory parameters, vital signs, 12-lead ECG results, C-SSRS, growth parameters, CBCL and LGPT. Study Day 1 for all safety analyses will be defined as the date of the 1st dose of study drug.

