### 5.6.3 Laboratory Values

Laboratory results will be summarized using Système International (SI) units, as appropriate. For all quantitative parameters listed in [protocol Section 9.5.1.5.3 Safety Assessments \(Laboratory Measurements\)](#), the actual value and the change from baseline to each postbaseline visit and to the end of treatment (defined as the last on-treatment value) will be summarized by visit using descriptive statistics. Qualitative parameters listed in [protocol Section 9.5.1.5.3 Safety Assessments \(Laboratory Measurements\)](#) will be summarized using frequencies (number and percentage of subjects), and changes from baseline to each postbaseline visit and to end of treatment will be reported using shift tables. Percentages will be based on the number of subjects with both nonmissing baseline and relevant postbaseline results.

Laboratory test results will be assigned a low/normal/high (LNH) classification according to whether the value was below (L), within (N), or above (H) the laboratory parameter's reference range. For each laboratory parameter, shift from baseline (LNH) to each postbaseline visit and at the end of treatment will be presented. Similar shift tables from baseline (LNH) to the highest/lowest postbaseline value will also be presented.

[Protocol Appendix 2 \(Sponsor's Grading for Laboratory Values\)](#) presents the criteria that will be used to identify subjects with treatment-emergent markedly abnormal laboratory values (TEMAV). Except for phosphate, a TEMAV was defined as a postbaseline value with an increase from baseline to a grade of 2 or higher. For phosphate, a TEMAV was defined as a postbaseline value with an increase from baseline to a grade of 3 or higher. The number and percentage of subjects with TEMAVs will be presented; each subject will be counted once in the laboratory parameter high and low categories, as applicable. Markedly abnormal laboratory values will be flagged in the subject data listings.

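### No laboratory table clearly counts children whose thyroid or IGF-1 results move from normal to abnormal on treatment

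*SAP*

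**What the plan says.** Core SAP 5.6.6, under the growth parameter heading, states: "The actual value and change from baseline in growth parameter (height, weight, TSH, fT3, fT4 and IGF-1) will be summarized by visit". Extension SAP 5.6.6 uses the same wording. Only height and weight get anything further, namely percentiles and z-scores. Protocol 9.7.1.8.6 likewise plans only change from baseline for these measures. The statistics come from Core SAP 5: "All descriptive statistics for continuous variables will be reported using mean, standard deviation (SD), median, minimum and maximum". They are produced by age, disease and inducer cohort.

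The subject-level laboratory rules are in Core SAP 5.6.3: "For each laboratory parameter, shift from baseline (LNH) to each postbaseline visit and at the end of treatment will be presented". The same section defines the markedly abnormal count: except for phosphate, "a TEMAV was defined as a postbaseline value with an increase from baseline to a grade of 2 or higher". For its list of parameters it points to Protocol 9.5.1.5.3, which reads "Clinical laboratory tests to be performed, including hematology, chemistry, and urinalysis, are summarized in" Table 3.

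**The concern.** Thyroid tests and IGF-1 belong to secondary endpoint 4 (growth and development) and are also among the SAP's safety variables. Thyroid dysfunction in a few children is an individual event. Group statistics do not say how many children are affected or whether they were normal at baseline. In a single-arm study with few scheduled thyroid tests, that count is the more informative summary.

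The SAP gives subject-level categories to most other safety domains:

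- shift tables for the routine laboratory tests
- clinically notable and abnormal criteria for vital signs
- QTc categories
- a normal/borderline/clinical class for the CBCL
- a shift to maximum severity for the C-SSRS

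For TSH, fT3, fT4 and IGF-1 it specifies none.

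**Working it through.** No figure in the plan is in dispute, so there is none to reproduce. The check is a comparison of texts, followed by an illustration of size.

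**Step 1. Do the laboratory rules reach these tests?**

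- *Protocol Table 3* lists hematology, chemistry and urinalysis parameters. TSH, fT3, fT4 and IGF-1 are absent.
- *Protocol Table 4 (schedule)* defines the routine row in a footnote: "Clinical laboratory tests include hematology, blood chemistry including lipid panel, and urinalysis". A separate row reads "Thyroid (TSH, fT3, fT4) and IGF-1 testing".
- *Core SAP 5.6* keeps the two groups apart: "Safety variables include TEAEs, clinical laboratory parameters, vital signs, 12-lead ECG results, C-SSRS, growth parameters, CBCL and LGPT".
- *The grading table* (Protocol Appendix 3, Core SAP 13.1, Extension SAP 13.2) has no row for any of the four tests. A TEMAV needs a grade, so none can arise.
- *The shift-table sentence* in Core SAP 5.6.3 speaks of each laboratory parameter and does not repeat the limit to Table 3.

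Exclusion from the TEMAV counts is therefore certain. Exclusion from the shift tables is the natural reading but is not stated.

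**Step 2. What would the planned statistics show?** Inputs: n = 160 (Core SAP 4). Assumed: k children go from TSH 2.5 to 10 mIU/L, and all others are unchanged.

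Mean change = k × (10 − 2.5) / 160.

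- k = 8 (5%): 60/160 = 0.375. SD of change = √{[8 × (7.5 − 0.375)² + 152 × 0.375²]/159} = √(427.5/159) = 1.64.
- k = 3 (about 2%): 22.5/160 = 0.14. SD of change = √{[3 × (7.5 − 0.14)² + 157 × 0.14²]/159} = 1.02.

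In both cases the median change is 0 and the maximum change is 7.5. The maximum and SD signal that something happened. Neither gives the count, and the maximum is the same for three children as for eight.

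**Step 3. The same question with natural variation.** Assumed: n = 160, the SD of change equals 1 baseline SD, and a fraction f of children shift by d SD (4,000 simulated trials per case). The mean shift is k × d / 160. The yardstick is how often the lower 95% confidence limit of the mean change lies above zero. The plan specifies no such interval for these parameters.

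| f (k) | d | Mean shift (SD) | Lower limit above 0 |
|---|---|---|---|
| 2.5% (4) | 1 to 3 | 0.025 to 0.075 | 5% to 12% |
| 5% (8) | 2 | 8 × 2/160 = 0.10 | 20% |
| 10% (16) | 1 to 3 | 0.10 to 0.30 | 22% to 87% |

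In the middle case the median shifts by about 0.07 SD on average.

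**Step 4. What would a count show?** The probability of at least one newly abnormal child in 160 is 1 − (1 − p)^160. It is 0.80 at p = 1%, 0.96 at p = 2% and above 0.999 at p = 5%.

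**The case against.** The case for leaving the plan alone has four parts.

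1. *More than averages is reported.* SD, minimum and maximum are planned, by cohort. In the example of Step 2, a maximum change of 7.5 would not read as no effect. This stands. A reader might infer that thyroid harm is visible only through the mean, and the documents do not support that. What is missing is the number of children and their baseline status.
2. *Exclusion from the shift tables is not stated.* The shift-table sentence could be read to include thyroid results, and the table shells are in a separate document that is not available here. This also stands, so the plan cannot be said to exclude these tests expressly. It leaves the matter open, and the surrounding text points toward exclusion.
3. *Adverse event reporting is a second route.* Protocol 9.5.1.5.1 requires the investigator to review every laboratory finding and says that an abnormality leading to intervention, or to withdrawal or withholding of study drug, should be considered an adverse event. Such cases would enter the TEAE tables, possibly also the special-interest group for laboratory abnormalities. A DMC also reviews safety data. The remaining gap is out-of-range results that led to no action and were not judged adverse events.
4. *The endpoint is delivered as defined.* Secondary endpoint 4 is change from baseline at Weeks 23 and 52, and the SAPs summarise it. A reader might infer that the endpoint fails in its purpose. The documents do not support that, because nowhere do they say the thyroid tests were included to count individual dysfunction.

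A missing grade is also not peculiar to thyroid: globulin has none either. Globulin is in Table 3, however, and so does get shift tables.

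**Conclusion.** The point holds as a gap in reporting, not as an error in the endpoint. As written, TSH, fT3, fT4 and IGF-1 get value and change summaries only. They can never be TEMAVs, and on the natural reading they are outside the low/normal/high shift tables. No specified laboratory table then says how many children normal at baseline became low or high. Outside the adverse event tables they are not counted.

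The size cannot be taken from the documents, which give no thyroid reference ranges, SDs or rates. The TSH values, the percentages affected and the SD of change used above are all assumptions. They show only that a small affected minority moves the mean and median little, while a count shows it directly. A count would not establish cause either: with no control arm, some children will cross a reference limit without any drug effect. A shift table at least shows movement in both directions.

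The change is worth making because it is cheap and brings these tests into line with the SAP's treatment of routine laboratory tests. The conclusion would fall away for the shift tables if the unseen table shells already include these four tests. Even then the SAPs should say so.

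**What to change.** Add to the growth parameter paragraph of Core SAP 5.6.6: *TSH, fT3, fT4 and IGF-1 will also be classified as low, normal or high against the laboratory's age-appropriate reference ranges. Shift tables from baseline to Week 23 and to end of treatment will be presented, with the number and percentage of children normal at baseline who become low or high.*

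Add the same text to Extension SAP 5.6.6, with Week 52 and end of treatment as the time points.

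The end-of-treatment column matters because thyroid testing is also scheduled at early discontinuation. Shifts to the highest and lowest postbaseline value are not needed in the core study. It has one scheduled on-treatment test (Visit 9, or the early discontinuation visit), so those tables would largely repeat the others.

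The cost is one addition to each SAP, four more parameters in existing shift-table programs, and a few more tables. No new samples are needed. Age-appropriate reference ranges for the four tests must be in the database.
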